## **INTRODUCTION AND PURPOSE:**

The purpose of this study is to assess the psychosocial effects of a novel web application (web app) called “immi” (short for ‘i am me’), designed to provide sexual and gender minority youth (SGMY) with tools for affirming their identities and coping with minority stress. Prior research demonstrates that interventions that focus on providing SGMY with resources for adaptively coping with minority stress have the potential to improve their mental health and wellbeing. However, few digital resources exist to address this need. The goal of the proposed research is to test whether this novel and scalable web-based intervention has the potential to impact key psychosocial outcomes among SGMY ages 13-19, such as coping self-efficacy and symptoms of anxiety and depression. Please see the Background section of this application for more information.

## **OBJECTIVES:**

Objective 1: To test whether SGMY randomly assigned to use the immi web app report significantly higher identity affirmation, subjective connectedness to the LGBTQ+ (Lesbian, Gay, Bisexual, Transgender, Queer/Questioning, and other sexual and gender minority identities) community, use of adaptive cognitive and behavioral coping skills, and psychosocial wellbeing (e.g. higher positive and negative affect, lower symptoms of depression and anxiety, and greater life satisfaction) than youth randomly assigned to a ‘resource list’ control group. The resource list control group will receive a list of technology-based psychosocial resources that are currently freely available to SGMY.

Objective 2: To assess how individual differences in usage and satisfaction with the immi web app relate to the outcomes listed in Objective 1, and to identify areas for further tool optimization. We will achieve this by linking web app usage data to outcome data, as well as through collecting quantitative and qualitative data measuring user satisfaction and suggestions for improvement.

## **BACKGROUND:**

Compared to their cisgender, heterosexual peers, sexual and gender minority youth (SGMY) are at increased risk of experiencing a wide variety of negative mental health outcomes. SGMY are twice as likely as their non-SGMY counterparts to report feeling sad or hopeless, and three times as likely to have considered attempting suicide. In one recent national survey, 65% of SGMY reported symptoms of moderate to severe depression as compared with 31% of their straight, cisgender peers.

The minority stress model provides a framework for understanding the higher prevalence of psychological distress and negative mental health outcomes for SGMY, as well as for identifying interventions to improve sexual and gender minority (SGM) mental health. Minority stress theory proposes that SGM health disparities can be explained in large part by discrimination from a homophobic and hostile culture,

---

 Centers for Disease Control and Prevention Youth Risk Behavior Survey (2017)

 Coping With Covid-19: How Young People Use Digital Media To Manage Their Mental Health (2021)

which creates stressors unique to minority identity, including harassment, victimization, internalized homophobia, and expectations of rejection. Efficacious mental health interventions for SGMY have focused on providing resources for coping with minority stress, including affirming SGM identities, teaching cognitive and behavioral coping skills, and strengthening supportive social connections.

While prior research suggests that interventions that include these components may improve the mental health of SGMY, interventions have primarily been delivered within the context of time intensive, in-person sessions, limiting their reach. Many SGMY face significant barriers to accessing affirming in-person services, an issue that has been exacerbated by the COVID-19 pandemic. Digital technologies can be utilized to help bridge this gap by meeting a pressing need within a medium in which youth are already seeking support. Over half of SGMY report spending over five hours a day online, and SGMY are more likely than those who identify as heterosexual to report going online for health information, including for support with depression (76% vs. 32%) and anxiety (75% vs. 36%). However, to date, there is little research examining the efficacy of web-based platforms for helping SGMY cope with minority stress.

The proposed research seeks to fill this need by testing the efficacy of a web app for SGM ages 13-19. This web app is designed to facilitate SGM identity affirmation, promote a sense of connectedness to the LGBTQ+ community, and encourage cognitive and behavioral coping skill practice. This tool was built by Hopelab, a nonprofit social innovation lab, in collaboration with CenterLink, an international nonprofit organization and member-based association of LGBTQ (Lesbian, Gay, Bisexual, Transgender, and Queer) centers serving their local and regional communities. The goal of the proposed research is to assess the efficacy of this web app for improving key psychosocial outcomes among SGMY, such as coping self-efficacy and symptoms of anxiety and depression.

---

 Meyer, I. H. (2003). Prejudice, social stress, and mental health in lesbian, gay, and bisexual populations: conceptual issues and research evidence. *Psychological bulletin*, 129(5), 674.

 Craig, S. L., Austin, A., & McInroy, L. B. (2014). School-based groups to support multiethnic sexual minority youth resiliency: Preliminary effectiveness. *Child and adolescent social work journal*, 31(1), 87-106.

 Craig, S. L., & Austin, A. (2016). The AFFIRM open pilot feasibility study: A brief affirmative cognitive behavioral coping skills group intervention for sexual and gender minority youth. *Children and Youth Services Review*, 64, 136-144.

**CHARACTERISTICS OF THE STUDY POPULATION:*****1. Target Population and Accrual:***

We will recruit 300 participants from across the United States, ages 13-19, who self-identify as sexual or gender minorities. To ensure that our results generalize to SGM of color, who face multiple forms of intersecting minority stress, we will over-recruit non-white participants such that they comprise approximately 75% of our sample (~225 participants). Non-Hispanic white participants will comprise approximately 25% of our sample (~75 participants). Participants will be recruited through social-media based advertisements posted on platforms such as Facebook, Tumblr, Instagram, Reddit, Jack'd, Grindr, and Twitter. Participants will be randomly assigned to a condition [experimental vs. control] in a 1:1 fashion. See the statistical analysis section for more details on statistical methods and theoretical justification for the sample size.

***2. Key Inclusion Criteria:***

Participants will be eligible if they:

1. Are between 13-19 years of age (inclusive)
2. Self-identify as a sexual or gender minority
3. Are English literate
4. Reside within the United States
5. Have access to a device that has internet access, a web browser, and SMS capabilities, such as a smartphone, computer, or tablet
6. Willingness to participate in study activities

Additionally, given that this is an online intervention, in order to be considered enrolled in the study, individuals must pass enrollment verification procedures which are detailed in the attached "SOP-Applicant Verification.pdf." If all criteria are met, participants will be randomized into a study arm and considered enrolled into the study.

**Justification**

We are testing the product with 13-19 year olds because the web app itself was designed in collaboration with young people in this age range, and the content of the app developmentally targets their specific questions and concerns. Additionally, this age range is critical for this research because adolescence is a pivotal period for sexual and gender identity development, and one in which SGM youth exhibit significantly higher levels of identity-related mental health problems compared to their straight cis-gender peers (Marshal et al., 2011). Thus, interventions aimed at affirming SGM identities and managing identity-related minority stress--such as the proposed intervention--have the potential for greatest impact when delivered to this age group. It is important to study this "vulnerable population" because they are at risk for negative cognitive, behavioral, and mental health outcomes. The development and testing of interventions targeted to this age group has the potential for significant gains in health for this age group.

The immi web app is specifically designed to teach cognitive and behavioral coping skills for responding to minority stress. We are proposing over-recruiting non-white (i.e., those who self-identify as at least one race or ethnicity other than white) participants because we want to ensure that our results are generalizable to those who face multiple forms of intersecting minority stress.

### **3. Key Exclusion Criteria:**

Exclusion criteria for enrollment into the study include:

1. Age younger than 13 or older than 19
2. Do not self-identify as SGM
3. Not English-literate
4. Reside outside of the United States
5. Do not have access to a device that has internet access, a web browser, and SMS capabilities, such as a smartphone, computer or tablet
6. Are not willing to participate in study activities

### **4. Subject Recruitment and Screening:**

We will reach the study population using social media ads on platforms including Facebook, Tumblr, Instagram, Reddit, Jack'd, Grindr, and Twitter, and other comparable social media platforms (see example copy and images in "Recruitment materials.pdf"). Social media platforms allow us to specify our audience based on socio-demographic characteristics (e.g., age, race/ethnicity) to increase their specificity to our population.

Ads will link interested individuals to a 5-10 minute uncompensated Qualtrics screener where they may verify their eligibility or email the team if they have questions. The screener survey will provide potential participants with basic information about the study purpose, procedures, and compensation. Individuals will then be asked for consent to take the screener. Those who consent will be asked questions to determine their eligibility, and asked to provide their first name, email address, and phone number. Those who do not consent to take the screener will be routed to a public site (e.g., Google).

All individuals who complete the screener will be asked if they would like to be contacted about other research studies in the future, then will be routed to a public site (e.g., Google). For those who are eligible based on their screener responses and pass the initial fraud verification process, we will email them with a link to the informed consent form. Individuals who consent will complete a 30- to 40-minute baseline survey. Compared to the gold standard (in-person interviewing), a limitation of online research – like mail and phone surveys – is the challenge of verifying a respondent's authenticity. Using best practices (see SOP-Applicant Verification.pdf), we will attentively reduce the likelihood of duplicative entries, bots, and/or catfishing (fake online personas). Verified participants will be randomized into one of the two study arms.

**Web-based recruitment screener:** The online survey is hosted by Qualtrics. It will include the eligibility script, consent/assent to be screened, and the screener questions. It will ask for the first name, email, and phone number of the applicant. We use Secure Socket Layer (SSL) encryption for online transfers of information, and data will be stored on Qualtrics' secure, HIPAA-compliant servers.

---

## **5. Early Withdrawal of Subjects:**

Participants are told in the consent form that they can withdraw from the study by contacting [name] at the University of Pennsylvania by email ([[contact]](mailto:[contact])).

Participants may also be withdrawn by the study PI at any time for the following reasons:

- A participant is flagged to have a duplicate or fraudulent registration during the fraud detection process. Fraudulent entries will not be counted towards study recruitment totals.
- Failure to follow study instructions
- Other circumstances in which a PI determines that continued study participation is not in the best interest of a participant
- The subject becomes incarcerated or placed in detention during the study
- Death of the subject

No further data collection will occur from the date the decision is made to permanently discontinue the subject from the study.

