## **STUDY DESIGN:**

The research activities involve a two-arm prospective RCT enrolling a sample of 300 SGMY (ages 13-19). After consent and completion of the online baseline survey, SGMY will be randomized to either the control or experimental condition (Control, n=150; Experimental, n=150). A self-completed online follow-up survey will be conducted at 4 weeks for all participants.

Participants randomized to the control group will be given access to a website that includes a list of freely available web-based resources for SGMY. They will have access to resources on this list for the 4-week active study period, but will not receive any engagement reminders, matching the conditions present in real world contexts in which web-based resource lists are available to SGMY.

Participants randomized to the experimental group will be given access to the study web app and will be encouraged to engage with the web app as much as they like over the four-week active study period. During the active study period, they will receive periodic reminders via SMS and/or email to visit the web app.

The goal of the proposed research is to test whether a novel and scalable web application (app) designed to provide SGMY with tools for affirming their identity and coping with minority stress has the potential to impact key psychosocial outcomes (e.g., coping self-efficacy and symptoms of anxiety and depression) among a sample of 300 SGMY.

Overall, the estimated data collection time for participants includes 10 mins for the initial recruitment, and two online surveys that are each approximately 30-40 mins. Thus, the total amount of time spent on the study activities (not including web app or online resource site usage) would be approximately 1-1.5 hrs. The amount of time spent using the web app will vary, depending on the interest and engagement of the participants. The web app is designed to facilitate delivery of SGMY identity affirming content and cognitive and behavioral coping skills exercises that average 5-10 minutes in length. However, the participants are free to use the guides as little or as much as they like. The amount of time experimental participants spend using the web app is unrelated to their compensation.

The study is funded for 8 months (Project Period: 07/01/2021 to 02/28/2022). Once consented, participants will be active in the study for 4 weeks.

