#### **4. Administration of Surveys and/or Process:**

We will collect survey data via online self-completed Qualtrics surveys administered at baseline and 4 weeks. Participants will enter their own responses to questions directly into the survey on their personal computer, smartphone or tablet.

Individuals who complete the screener survey and are eligible will be sent a link to the informed consent form. Those who provide their consent will complete a baseline assessment which will take approximately 30-40 minutes. At the end of the 4-week active study period, participants will complete an online survey to assess key psychosocial outcomes. This follow-up survey will take participants approximately 30-40 minutes to complete.

The incentive for completing the baseline survey is \$30 and the follow-up survey incentive is \$40. These incentives are small enough to avoid coercion, yet sufficiently substantial to promote retention. In order for interventions to be evaluated as potential best evidence-based interventions through CDCs Prevention Synthesis Research activity, data must be available for at least a single follow-up time point for at least 70% of participants. As described below, a detailed retention plan for the study will draw on previously successful retention protocols to achieve at least an 80% retention rate for the follow-up survey.

If a participant does not complete their follow-up survey by Day 31, we will send a reminder message via email, SMS, or direct message via social media (depending on the participant's communication preferences). The participant will be recontacted using the same methods on Day 35, 39, and 42 if they still have not completed the survey. Each contact will be logged in a spreadsheet.

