### **6. Subject Follow-up:**

This study involves one follow-up at 4 weeks after baseline survey completion. A detailed retention plan (see "SOP-Participant Retention.pdf") will draw on our prior successful protocols with hard to reach populations to achieve ≥80% retention rate for the 4-week assessment. We will use best practices to retain participants while being sensitive to undue disclosure of SGMY participating in the study. Every effort will be made to reduce attrition as retention is critical to our study efforts. Correlates of missing data and attrition will be carefully examined. We will compare those who completed the follow-up survey with those who did not on key predictors from the baseline assessment to check for possible sample bias.

Participants will be discontinued from the study in the event that we are notified that they are imprisoned, committed to a mental hospital, hospitalized for long term care, admitted to a drug/alcohol residential program, or a residential living facility.

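### Withdrawal for not following study instructions ends all data collection after randomisation, so a week-4 outcome that could still be sought is lost; the likely bias is small

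*Combined protocol and SAP*

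**What the plan says.** - **Early Withdrawal of Subjects** introduces its list with "Participants may also be withdrawn by the study PI at any time for the following reasons". One entry is "Failure to follow study instructions", given without a definition, threshold or example. The section closes: "No further data collection will occur from the date the decision is made to permanently discontinue the subject from the study". It makes no exception for the outcome survey.
- **Subject Follow-up** states: "This study involves one follow-up at 4 weeks after baseline survey completion". It targets retention of at least 80%, commits to keeping attrition low, and adds: "We will compare those who completed the follow-up survey with those who did not on key predictors from the baseline assessment". It also has its own list of discontinuation grounds (imprisonment and several kinds of institutional admission), in mandatory wording.
- **Administration of Surveys and/or Process** sends a first reminder if the Day-28 survey is not done by Day 31, and then: "The participant will be recontacted using the same methods on Day 35, 39, and 42 if they still have not completed the survey".
- **Study Design** makes app use optional: "the participants are free to use the guides as little or as much as they like". The experimental arm is prompted to visit the app. Controls have access to the resource list "but will not receive any engagement reminders".
- **Statistical Analysis** describes the main comparison as intent-to-treat at week 4, adjusted for baseline, and names no method for missing outcomes. It plans for 300 participants, up to 35% lost through non-compliance or attrition, and about 97 left per group.

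**The concern.** Withdrawal on this ground is a judgement made after randomisation, and under the rule as written it also removes the participant's only chance to supply an outcome. Death or withdrawn consent rules out a further survey. Failing to follow an instruction does not, because the person can still open a link and answer. The plan therefore gives up an outcome that it could still seek, which works against both the intent-to-treat analysis and the aim of limiting attrition.

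At stake is comparability. If the people removed differ from those retained, and do so by a different amount or in a different proportion in the two arms, the week-4 contrast no longer compares the groups as randomised. Adjustment for baseline values corrects this only so far as the difference was already visible at baseline.

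**Working it through.** **The plan's own figure.** 300 × (1 − 0.35) / 2 = 97.5, which reproduces the figure of about 97 per group. The 35% already includes non-compliance, so removals on this ground sit inside the allowance and no further deduction from 97 is due. With a two-sided 5% test (assumed, since the plan states no alpha), 97 per group gives 93.4% power for d = 0.50.

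**Bias formula.** Let w be the share of an arm removed on this ground, and let g be the retained-minus-removed gap in the outcome, in SD units. The retained mean exceeds the full-arm mean by w × g, so the bias in the contrast is

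w₁g₁ − w₀g₀.

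Other non-response is left out, and everyone removed is taken to be someone who would have answered. The documents give no value for w or g, so every value below is an assumption.

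**Case A: equal removal rates, different gaps.** Bias = w × (g₁ − g₀), with w from 2% to 5% (3 to 7.5 of 150).

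| w | Gap difference | Bias (SD) | Share of 0.50 |
|---|---|---|---|
| 0.02 | 0.1 | 0.002 | 0.4% |
| 0.02 | 0.4 | 0.008 | 1.6% |
| 0.05 | 0.1 | 0.005 | 1% |
| 0.05 | 0.4 | 0.020 | 4% |

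**Case B: unequal removal rates, same gap.** Bias = (w₁ − w₀) × g, with a 5-point difference (7.5 of 150).

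- g = 0.25: 0.05 × 0.25 = 0.0125 SD, or 2.5% of 0.50.
- g = 1.0: 0.05 × 1.0 = 0.05 SD, or 10% of 0.50.

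**Case C: equal rates and equal gaps.** Bias = 0.

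**Baseline adjustment.** If the gap is already present at baseline and the baseline to week-4 correlation is r, a fraction 1 − r of the bias remains. With r assumed to be 0.4–0.7, Case A becomes 0.02 × 0.1 × 0.3 = 0.0006 to 0.05 × 0.4 × 0.6 = 0.012 SD. If the gap arises only after randomisation, adjustment removes none of it.

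**Type I error (nominal two-sided 5%).**

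- Bias 0.02 SD, 120 per arm (80% retention): the unadjusted standard error is √(2/120) = 0.129, and the error rate is about 5.3%. With r = 0.7 the standard error is √(2 × 0.51/120) = 0.092 and the rate about 5.5%, if adjustment leaves the bias intact.
- Bias 0.05 SD, 97 per arm: the unadjusted standard error is √(2/97) = 0.144, and the rate is about 6.4%. With r = 0.6 and the bias left intact, it is about 7.2%.

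**The case against.** The strongest reply is that little is left for this ground to act on. App use is optional, so the instructions that remain are mainly to register an account and to complete the follow-up survey. Someone who does not complete the survey has no outcome whether or not the investigator withdraws them. The wording is also permissive, and a cited SOP or the consent text, neither of which was available, may define the ground. All of this stands, and it is why the point is minor. It does not remove the rule that collection stops once the decision is made, and that rule is what loses the outcome.

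A reader might draw stronger conclusions that the documents do not support:

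- **Low app use leads to withdrawal.** Study Design leaves the amount of use to the participant, so low use is not clearly a breach.
- **The trial loses power.** Subtracting these removals from 97 counts them twice, because the 35% allowance already includes non-compliance.
- **Removals will be unbalanced.** Only one arm is prompted to engage, so balance is not assured, but nothing links those prompts to withdrawals on this ground.
- **The bias could be large.** A 20-point one-sided difference with a gap of 0.5–1.0 SD would give 0.10–0.20 SD and, at 97 per arm unadjusted, a type I error of about 11–29%. The text does not prevent such use, but nothing predicts it.
- **Subject Follow-up leaves data collection open.** The closing sentence of Early Withdrawal most naturally governs those discontinuations too.
- **The clause calls for an imputation plan.** How missing outcomes are handled is a matter for the 20–35% general attrition, separate from this clause.

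**Conclusion.** The point holds as a minor design weakness. The plan lets a post-randomisation judgement end outcome collection for people who could still be asked for their single week-4 response. Under the assumptions shown, the bias is 0.002–0.02 SD with equal removal of 2–5% per arm, and 0.013–0.05 SD with a 5-point difference in removals. At the top of that second range, the type I error at 97 per arm is about 6.4% unadjusted, and somewhat higher if adjustment narrows the standard error without removing the bias.

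Calling this small is a judgement. It rests on assumed rates and on how few instructions there are to breach. Some of those withdrawn would not have answered in any case, which reduces the effect further.

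**What to change.** In Early Withdrawal of Subjects, state that withdrawal for failure to follow study instructions does not end outcome collection. These participants would still be sent the existing Day-28 survey and the Day 31, 35, 39 and 42 reminders, unless they withdraw consent or are confirmed as duplicate or fraudulent. They stay in their randomised arm for analysis, and withdrawals with reasons are reported by arm. The other grounds in that section are not touched by this proposal.

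Separately, reconcile the two discontinuation lists in Early Withdrawal of Subjects and Subject Follow-up. They name different grounds, and one is permissive where the other is mandatory. This review takes no position on which grounds should apply.

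The cost is a few sentences and, at the assumed 2–5%, a survey link and up to four reminders for 3 to 7.5 participants per arm. Those messages carry the disclosure risk described under Risks and would stay under its safeguards. The consent text may need a matching line. The sample size does not change.
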